3.3.2.4 Menstruation Heaviness and Menstruation-related Quality of Life

MBQ will be summarized descriptively over time, including change from baseline for individual subscales (heaviness, quality of life, irregularity, and pain) and total score. Pictorial Blood Assessment Chart (PBAC) scores will be summarized descriptively over time. If the number of female patients of childbearing potential is too low to provide reliable summaries, the data will be listed and presented in individual patient plots where applicable.

3.3.3 Subgroup Analyses

Additional descriptive summaries of both treated bleeds and all bleeds will be computed for various subgroups of the study. The summaries will include subgroup ABR and its 95% CIs. The main pre-specified subgroups are as follows:

- Age: 0 to <2, 2 to <6, 6 to <12, 12 to <18, 18 to <65, ≥65 years
- Race: Asian, Black or African American, White, Other
- Hemophilia severity: mild, moderate
- Number of target joints at study entry: no target joint, any target joint
- Previous treatment regimen: prior episodic, prior prophylactic
- Prior FVIII inhibitor: Yes/No
- Female patient: Yes/No
- Dosing regimens at enrolment: 1.5 mg/kg QW, 3 mg/kg Q2W, 6 mg/kg Q4W

Note that due to the likely small sample sizes, subgroup analyses will be highly susceptible to variability and should therefore be interpreted with caution.

Emicizumab —F. Hoffmann-La Roche Ltd 12/Statistical Analysis Plan BO41423 Additional region- and/or country-specific analyses may be performed to support regulatory submissions as needed.

3.4 PHARMACOKINETIC ANALYSES

The PK endpoint for this study is the exposure (C_{trough}) of emicizumab in patients assessed prior to drug administration on Day 1 and at the following timepoints:

- Every week during Weeks 1-4 on emicizumab
- Every four weeks during Weeks 5-45 on emicizumab
- Every twelve weeks from Week 49 thereafter while continuing on emicizumab until the end of the study

Plasma concentrations of emicizumab will be presented descriptively, including arithmetic and geometric means, median, range, standard deviations, and coefficients of variation.

Nonlinear mixed-effects modeling may also be used to analyze the dose-concentrationtime data of emicizumab following SC administration and estimate population PK parameters. If conducted, these analyses will be reported in a dedicated report.

3.5 BIOMARKER ANALYSES

Change over time in the PD parameters: activated partial thromboplastin time (aPTT), prothrombin time (PT)/ international normalized ratio (INR), reported FVIII activity (emicizumab sensitive and insensitive), FVIII protein level, and thrombin generation as well as fibrinogen, D-dimer and PF1+2 levels will be presented using summary statistics, including arithmetic and geometric means, median, range, standard deviations, and coefficients of variation. In addition, individual patient plots will be provided. Bone and joint health will be summarized.

3.6 IMMUNOGENICITY ANALYSES

3.6.1 Anti-Emicizumab Antibodies

The immunogenicity analyses for emicizumab antibodies will be performed on the immunogenicity population.

The numbers and proportions of ADA-positive patients and ADA-negative patients during both the treatment and follow-up periods will be summarized. Patients are considered to be ADA-positive if they are ADA-negative at baseline or have no baseline value but develop an ADA response following study drug administration (treatment-induced ADA response), or if they are ADA-positive at baseline and the titer of one or more post-baseline samples is at least 4-fold greater than the titer of the baseline sample (treatment-enhanced ADA response). Patients are considered to be ADA-negative if they are ADA-negative at baseline or have no baseline value and all post-baseline samples are negative, or if they are ADA-positive at baseline but do not

Emicizumab — F. Hoffmann-La Roche Ltd 13/Statistical Analysis Plan BO41423 have any post-baseline samples with a titer that is at least 4-fold greater than the titer of the baseline sample (treatment unaffected).

3.6.2 Factor VIII Inhibitors

The number and proportion of patients who develop anti-FVIII inhibitors (titer ≥ 0.6 BU/mL) following study drug administration will be summarized.

3.7 SAFETY ANALYSES

Safety will be assessed through descriptive summaries of adverse events, laboratory test results (serum chemistry and hematology including complete blood count with differential and platelet counts), ECGs, vital signs, ADAs, and de novo FVIII inhibitors. To evaluate the overall safety of emicizumab, the incidence of adverse events will be summarized and presented by System Organ Class mapped term, appropriate thesaurus level, and toxicity grade. For clinical laboratory data, summary statistics will be presented. In addition, shift tables describing changes from baseline will be presented using the WHO Toxicity Grading Scale.

3.7.1 Exposure to Study Medication

Information on study drug administration will be summarized by duration and cumulative dose. In addition, treatment exposure will be summarized including delays and interruptions.

Patient withdrawals from study treatment will be reported in listings and summary tables.

3.7.2 Adverse Events

To evaluate the overall safety of prophylactic emicizumab, adverse events will be summarized and presented by System Organ Class mapped term, appropriate thesaurus level, and toxicity grade (WHO Criteria). All AEs will be coded using the current version of Medical Dictionary For Regulatory Activities (MedDRA) at the time of each database closure (interim and primary analysis). For the purpose of summarization, a patient is counted once in a system organ class or preferred term if the patient reported one or more events in that system organ class or preferred term. Percentages will be based on the number of patients overall.

The total number and percentage of patients with at least one adverse event (AE) and total number of AEs will be summarized. Separate AE summaries for serious adverse events (SAEs), adverse events of special interests (AESIs), severity, relatedness, and discontinuation/modification will be provided.

An overall summary of adverse events (including SAEs, AESIs, AEs leading to drug discontinuation, and deaths), which tabulates the number and percentage of patients who experienced any or serious adverse events and the number and percentage of patients who died, will be provided.

Emicizumab —F. Hoffmann-La Roche Ltd 14/Statistical Analysis Plan BO41423 For adverse events with a missing intensity, seriousness, or relationship, the worst case will be assumed and the adverse events will be considered life-threatening (Grade 4) or serious.

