Exploratory PD biomarkers and safety biomarkers will be collected within 24 hours but no later than 48 hours of a treated bleed.

Emicizumab—F. Hoffmann-La Roche Ltd 29/Protocol BO41423, Version 3

[figure not shown]
After 24 weeks on prophylactic emicizumab, patients with suboptimal bleed control will be offered the option to increase their dose to 3 mg/kg QW, with approval from the Medical Monitor, if the protocol-defined criteria of suboptimal response is met (see Section 4.3.2).

Interim data reviews may be performed at various timepoints (e.g., for regulatory submissions), and the primary analysis for all patients will be conducted after 50 patients with moderate hemophilia A have completed 52 weeks of emicizumab treatment, are lost to follow-up, or have withdrawn, whichever occurs first. The primary analysis will occur at the specified time regardless if no patients with mild hemophilia A are enrolled; however, enrollment will be left open for patients with mild hemophilia A in order to enroll approximately 20 such patients. The total number of patients in the study might slightly exceed 70 patients depending on the number of female patients enrolled. Ideally, at least 5 female patients will be enrolled. If these are not recruited within the pool of 70 patients, the enrollment will remain open until they are enrolled or until the cutoff date of primary analysis, whichever occurs sooner. Note that all patients will be included in the primary analysis irrespective of their follow-up time. After the primary analysis, patients will continue to receive emicizumab according to the Roche Policy on post study drug access until emicizumab is approved and accessible to patients commercially.

Patients who discontinue study drug prior to end of study will return to the clinic for a safety follow-up visit, 24 weeks after the last dose of study drug. Patients who complete or discontinue from the study will return to the clinic for a study completion/discontinuation visit (see Appendix 1 and Appendix 2).

Figure 1 presents an overview of the study design. The schedules of activities are provided in Appendix 1 and Appendix 2.

Figure 1 Study Schema

QW = once a week; Q2W = every 2 weeks; Q4W = every 4 weeks.

Note: Patients who discontinue study drug prior to end of study will return to the clinic for a safety follow-up visit 24 weeks after the final dose of study drug.

^a Interim data reviews may be performed at various timepoints.

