6.4 SAFETY ANALYSES

The safety analyses population will be based on all patients who received at least one administration of emicizumab. Safety will be assessed through descriptive summaries of adverse events, laboratory test results (serum chemistry and hematology including complete blood count with differential and platelet counts), ECGs, vital signs, ADAs, and de novo FVIII inhibitors. To evaluate the overall safety of emicizumab, the incidence of adverse events will be summarized and presented by System Organ Class mapped term, appropriate thesaurus level, and toxicity grade. For clinical laboratory data, summary statistics will be presented. In addition, shift tables describing changes from baseline will be presented using the WHO Toxicity Grading Scale.

Summaries will be presented overall, by dosing regimen, and, if applicable, by disease severity. Further details will be provided in the SAP.

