2.4 DETERMINATION OF SAMPLE SIZE

The overall sample size of approximately 70 patients (approximately 50 patients with moderate disease and approximately 20 patients with mild disease) is based primarily on feasibility and clinical considerations, taking into account the limited number of patients with non-severe hemophilia A. This sample size is expected to provide statistically robust point estimates with meaningfully narrow confidence intervals in the overall group of enrolled patients, at the time of the primary analysis or at the time of interim analysis appropriate for regulatory submissions, assuming the same efficacy across dosing regimens.

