3.1 ANALYSIS POPULATIONS

3.1.1 All Patients Population

The All patients population includes all patients enrolled in the trial. This population will be used to describe demographic and baseline characteristics.

3.1.2 Treated Population

The Treated population corresponds to all patients who received at least one dose of emicizumab. This population will be the primary population for efficacy and safety analyses.

Emicizumab —F. Hoffmann-La Roche Ltd 9/Statistical Analysis Plan BO41423

3.1.3 Pharmacokinetic-Evaluable Population

The PK-Evaluable population includes all patients who have received at least one dose of emicizumab and have at least one post-baseline emicizumab plasma concentration result.

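### SAP 3.7 does not carry forward the protocol's safety summaries by dosing regimen and severity, and reports AE incidence only as a pooled percentage, with no exposure-adjusted rate

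*SAP*

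**What the plan says.** Protocol 6.4 commits the safety analysis to three views: "Summaries will be presented overall, by dosing regimen, and, if applicable, by disease severity". It leaves the details to the SAP. The condition attaches to severity only; the regimen view is unconditional.

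SAP 3.7 to 3.7.5 name neither breakdown. For AEs, SAP 3.7.2 plans this: "The total number and percentage of patients with at least one adverse event (AE) and total number of AEs will be summarized". Each patient counts once per system organ class or preferred term, and "Percentages will be based on the number of patients overall". SAP 3.1.2 defines the Treated population (at least one dose) and says "This population will be the primary population for efficacy and safety analyses".

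Exposure is summarised separately, in SAP 3.7.1: "Information on study drug administration will be summarized by duration and cumulative dose". SAP 3.2 adds observation time and duration of follow-up. Neither document combines these with AE counts. By contrast, the bleed model in SAP 3.3.2.1 uses each patient's time in the study as an offset.

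SAP 3.3.3 defines severity and dosing-regimen subgroups, but for bleeds only: "Additional descriptive summaries of both treated bleeds and all bleeds will be computed for various subgroups of the study".

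On follow-up, Protocol 3.1 states "Note that all patients will be included in the primary analysis irrespective of their follow-up time". Protocol 3.3.2 sets the primary cut-off at 52 weeks after the last moderate patient is enrolled. Enrolment of mild patients is left open. If five women are not found among the 70 patients, enrolment of women may continue up to the cut-off.

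**The concern.** Two gaps reinforce each other. First, the SAP is where the protocol's safety tables should be specified, and two of the three promised views are missing from it. Second, AE incidence is a cumulative percentage that ignores time at risk, in a design that lets time at risk differ by severity.

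This touches the study's own safety question. Protocol 3.1 explains that observation to the primary analysis was lengthened because these patients have residual FVIII of at least 1% and longer safety data are wanted. Protocol 1.3 discusses a theoretical thrombotic risk of emicizumab added to residual FVIII. Mild patients have the most residual FVIII (above 5% and below 40%), they are the smaller group (about 20 of 70), and the cut-off does not wait for them. As written, the AE tables would not show their experience separately or relate it to their exposure.

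**Working it through.** The plan gives no AE rate, interval width or power to reproduce. Its one relevant figure, the sample size, adds up: 50 + 20 = 70. Inputs from the documents are 50 moderate and 20 mild patients (SAP 2.4), a 52-week cut-off tied to moderate patients (Protocol 3.3.2), and a study length of about 27 months with up to 4 weeks of screening and a 24-week safety follow-up (Protocol 3.2). AE risks and mild follow-up times are not in the documents; they are assumptions, shown as ranges.

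**1. How far follow-up could spread.** 27 months = 27 × 365.25 / 12 / 7 = 117.4 weeks. Subtracting 4 weeks of screening and 52 of treatment leaves at most 61.4 weeks for enrolment, or 37.4 if the 24-week safety follow-up also falls inside the 27 months. The earliest patients could then have 52 + 37.4 = 89.4 to 52 + 61.4 = 113.4 weeks at the primary cut-off. A late mild or female patient has no stated minimum.

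**2. Dilution by pooling.** Exact (Clopper-Pearson) 95% intervals for events occurring only in mild patients:

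| Mild events | Of 20 mild | Of all 70 |
|---|---|---|
| 1 | 5.0% (0.1 to 24.9) | 1.4% (0.0 to 7.7) |
| 3 | 15.0% (3.2 to 37.9) | 4.3% (0.9 to 12.0) |

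**3. Effect of shorter mild follow-up on the pooled percentage.** Assume the same constant hazard in both groups: λ = −ln(1 − p) / 52 per week, where p is the 52-week risk. Crude incidence after t weeks is 1 − exp(−λt). The pooled value is (50 × moderate + 20 × mild) / 70.

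Worked example: p = 20% gives λ = 0.2231 / 52 = 0.00429. With 12 weeks of mild follow-up, mild crude incidence is 1 − exp(−0.0515) = 5.0%, and the pooled value is (50 × 20.0 + 20 × 5.0) / 70 = 15.7%.

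Pooled crude incidence, with moderate patients followed for 52 weeks:

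| Assumed 52-week risk | Mild 12 wk | Mild 24 wk | Mild 36 wk | Mild 52 wk |
|---|---|---|---|---|
| 5% | 3.9% | 4.2% | 4.6% | 5.0% |
| 10% | 7.8% | 8.5% | 9.2% | 10.0% |
| 20% | 15.7% | 17.1% | 18.4% | 20.0% |
| 50% | 39.9% | 43.5% | 46.6% | 50.0% |

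With 52 weeks in both groups there is no distortion. If moderate patients instead had 75 weeks, the 20% row would read 21.1%, 22.5%, 23.7% and 25.4%. Against the 52-week risk, the crude figure can therefore be too low or too high.

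**4. Why a severity split alone is not enough.** Let the mild hazard be double the moderate hazard, with p = 20% in moderate patients followed for 52 weeks (crude 20.0%). Mild crude incidence is 1 − exp(−2λt):

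- 12 weeks: 9.8%
- 24 weeks: 18.6%
- 26 weeks: 20.0%
- 52 weeks: 36.0%

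At 26 weeks the two columns agree although the hazard is doubled. This holds for any assumed risk, because 2λ × 26 = λ × 52. First-event rates per 100 years of 52 weeks would be 100 × 0.2231 = 22.3 in moderate and 44.6 in mild patients, so a rate shows the difference.

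**The case against.** The strongest reply is that a patient-count percentage is a legitimate statistic in a single-arm, purely descriptive study, and that neither document promises exposure-adjusted rates. The denominator sentence does not forbid further columns. The severity view is conditional in Protocol 6.4, and the same sentence is reproduced in the synopsis in SAP Appendix 1. AEs of special interest, including thromboembolic events and thrombotic microangiopathy, are reported to the sponsor within 24 hours and summarised separately. Total AE counts and exposure are both reported, so an approximate overall rate could be worked out. All of this is fair, but it does not close the gap. The synopsis is a copy from protocol version 2 that itself defers to the SAP, so it specifies no table. The regimen view is unconditional. The SAP finds severity applicable for bleeds and gives no reason for leaving it out for safety. A reader could not reconstruct rates by severity.

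Several stronger readings are tempting, and the documents do not support them:

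- **That the SAP deliberately dropped the split.** The text shows only that SAP 3.7 does not carry it forward.
- **That follow-up will be very unequal.** Mild patients may enrol from the outset, and no accrual pattern is given. By the final analysis, patients who continue treatment have at least 52 weeks, so the imbalance mainly concerns the interim and primary analyses.
- **That crude percentages understate risk.** Step 3 of the working shows that the direction depends on follow-up.
- **That mild patients will look safer.** With no mild column they cannot; the present problem is pooling. That bias could arise only if crude percentages were split by severity without rates.
- **That zero-event upper limits (16.8% for 20 patients, 5.1% for 70) prove the exposure point.** They depend on n alone.
- **That results cannot be set against earlier emicizumab studies.** How those studies reported AEs is not in the documents, and no such comparison is planned.
- **That a thrombotic risk is established.** Protocol 1.3 calls it theoretical and concludes that the data do not suggest an increase.

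**Conclusion.** The point holds as a gap between protocol and SAP, together with a cheap improvement in method. SAP 3.7 omits the regimen tables that Protocol 6.4 promises outright and the severity tables that it promises conditionally. SAP 3.7.2 gives AE incidence only as one pooled percentage of Treated patients, in a design with no minimum follow-up at the primary analysis.

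The dilution rests only on the planned group sizes: an event confined to mild patients appears at 20/70, or about 29%, of its proportion in that group. The exposure effect rests on assumed constant hazards and assumed mild follow-up. It ranges from none at equal follow-up to complete masking of a doubled hazard at 26 versus 52 weeks. Nothing numerical in the plan is wrong, and the change should be made before the next database closure rather than treated as a fatal defect.

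**What to change.** In SAP 3.7, state that AE tables are shown overall, by dosing regimen and by disease severity, each column with its own N and total patient-years. The regimen and severity categories in SAP 3.3.3 can be reused. If severity tables are judged not applicable, for example because very few mild patients enrol, say so and give the rule.

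In SAP 3.7.2, keep the percentages and add rates per 100 patient-years with exact Poisson 95% confidence intervals, at least for any AE, serious AEs and each AE of special interest. Define the person-time used, and say whether the numerator is first events or all events. Apply the same layout at the interim, primary and final analyses.

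The cost is a few extra rows and columns from data already collected. Mild-group intervals will be wide. For illustration, 20 mild patients followed for 26 weeks give 20 × 26 / 52 = 10 patient-years. One event is then 10 per 100 patient-years, with exact Poisson limits for a count of 1 of 0.0253 (χ² 0.025 quantile, 2 df, halved) and 5.572 (χ² 0.975 quantile, 4 df, halved), that is 0.25 to 55.7 per 100 patient-years. That width states honestly how little would be known about the mild group.

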3.7.3 Laboratory Data

For clinical laboratory data, which were collected from local laboratories, summary statistics in SI units will be presented. Laboratory data not collected in SI units will be converted to SI units as applicable. In addition, shift tables describing changes from baseline will be presented using the WHO toxicity grading scale.

Data on the impact of immunogenicity (ADAs) on safety, efficacy, and/or clinical pharmacology and pharmacokinetics will be summarized using standard language/terminology (Shankar et al. 2008).

3.7.4 Vital Signs

Vital signs will be summarized using mean change from baseline tables over time. Measurements consist of heart and respiratory rate, temperature, and systolic and diastolic blood pressure.

